8.1.2 Form

The BVD-523 drug product is an oral capsule containing BVD-523 drug substance encapsulated in a hard gelatin capsule. The capsule dose strength intended for the clinical studies is 150 mg (yellow) as the free base content. The capsules will be provided in 30-count white HDPE bottles.

8.1.3 Storage and Stability

Bottles of BVD-523 will be stored at controlled room temperature (15°C-25°C) environment under temperature monitoring in a location with access limited to authorized study personnel.

BVD-523 drug product lots retest dates are driven by real-time stability. BioMed Valley Discoveries, Inc. will provide a note to file stating the retest date for each lot shipped. The site will be responsible to manage inventory and track retest dates. When a new retest date is due, the site will request to BioMed Valley Discoveries, Inc. or designee to issue an updated retest

date note to file to the site

8.1.4 **Compatibility**

8.1.5 **Handling**

Qualified personnel, familiar with procedures that minimize undue exposure to themselves and the environment, should undertake the preparation, handling, and safe disposal of the chemotherapeutic agent in a self-contained and protective environment.

8.1.6 **Availability**

BVD-523 drug product is stored at Catalent Pharma Solutions (CPS) in Kansas City, MO and will be shipped from this location to the clinical investigational site(s). All drug product remaining at the site will be destroyed at the end of the study in accordance with the site local guidelines and policies.”

8.1.7 **Preparation**

30-count bottles of BVD-523 drug product capsules will be distributed.
Site pharmacies will be responsible for:

1. Dispensing enough drug product to each subject.
 - a. Cycles 1-2: 1 extra day of drug.
 - b. After Cycle 2: 2 extra days of drug.
2. Affixing an appropriate label to the bottles of BVD-523 dispensed to enrolled subjects.
 - a. The label must contain a pharmacy-dispensed unique bottle number (as per their institution’s policy).

8.1.8 **Administration**

BVD-523 drug product will be taken orally by enrolled study subjects twice a day at the dose and as outlined on dosing instruction sheets provided to each subject. BVD-523 should be taken at the same time each day on an empty stomach (i.e., fasting), either 30-60 minutes before food or 2hrs after food, with 8 oz of water (juice, coffee, tea or soda is not allowed.). All capsules should be consumed in 10 minutes or less.

8.1.9 **Ordering**

As each site is initiated, the investigator or appropriate investigator-designee will order adequate supply of capsules (150 mg) to allow for dose escalations/reductions, as appropriate. Sites may request resupply of study drug as needed.

8.1.10 **Accountability**

The investigator, or a responsible party designated by the investigator, should maintain a careful

record of the inventory and disposition of the agent using the NCI Drug Accountability Record Form (DARF) or another comparable drug accountability form. (See the NCI Investigator's Handbook for Procedures for Drug Accountability and Storage.)

8.1.11 Destruction and Return

Any opened bottles of BVD-523 will be destroyed according to local policies and guidelines. Unopened, unused bottles containing the 30-count capsules will be destroyed at the end of the study in accordance with institutional SOPs.

BIOMARKER, CORRELATIVE, AND SPECIAL STUDIES

9.0 LABORATORY CORRELATIVE STUDIES

BVD-523 is expected to inhibit downstream signaling through ERK. Tumor biopsies are expected to be obtained 7-28 days prior to the first treatment and 12-16 days following the initial treatment in order to facilitate ERK signaling analysis, mutation analysis, sequencing, and cell line development.

The sequence as to preference of site selection for the pre- and post- treatment biopsies is: (1) biopsies of the same lesion, (2) different sites within the same organ, (3) different organs. While incisional or excisional biopsies are preferred, we anticipate that many patients will need to undergo imaging guided core needle biopsies of organs such as the liver. Sufficient biopsy material to provide at least 23 unstained paraffin embedded slides and extra fresh tissue from the pre- treatment biopsy and 13 unstained paraffin embedded slides and extra fresh tissue from the post-treatment biopsy is required. If imaging guided core needle biopsies are necessary, three to four specimens using an 18-gauge needle are required to obtain sufficient biopsy material from the pre-treatment biopsy. Two to three specimens using an 18-gauge needle are required to obtain sufficient biopsy material from the post-treatment biopsy. Blocks or sufficient unstained slides may be sent for processing; blocks are preferred. If the patient had a previous biopsy, material from that biopsy can be used for GNAQ and GNA11 testing (10 slides needed) and only enough biopsy material for 13 unstained paraffin embedded slides and extra fresh tissue is required from the pre-treatment biopsy.

Archival tissue from a biopsy taken within 6 months prior to the first study treatment may be used in place of a pre-treatment biopsy at the discretion of the PI

The biopsy specimens will be used for the following pharmacodynamic correlates:

1. Analysis of changes in ERK signaling such as pRSK, DUSP, cyclin D and others. This will be performed in conjunction with [name]'s lab at MGH.

2. Determination of the presence or absence of GNAQ and GNA11 activating mutations in the metastatic tumor. This will be performed on unstained paraffin embedded material derived from pre treatment biopsy or the initial biopsy confirming metastatic disease by a combination of PCR, HPLC and DNA sequencing.

3. Whole exome sequencing and RNA seq. This will be performed in collaboration with the Broad institute. There is a lack of knowledge about the genetic drivers of Uveal melanoma and this study will allow for an exploration of these on and off MAPK targeted therapy.

4. Routine histopathology (H+E staining)

5. Development of PDX: Tissues obtained from fresh biopsies will be used to generate patient derived xenografts and cell lines to evaluate mechanisms of drug resistance.

Procedure:

Ideally pre-and post-biopsies should be from the same lesion and otherwise from lesions in the same organ. If not possible, then biopsy of the lesions in different organs will be permitted.

One specimen of fresh tissue sample should be sent to [name] at DFCI Medical Oncology Labs as soon as possible after tissue is available. It will be necessary to coordinate with [name] ([contact]) and copy [contact]) for each biopsy in order to ensure that the sample can be processed immediately after the biopsy. The rest of the tissue specimens (fixed) should be sent to [name]'s lab at MGH for further analysis. Tissue processing at the MGH Med Onc lab will require sufficient biopsy material to provide at least 23 unstained paraffin embedded slides from the pre- treatment biopsy and 13 unstained paraffin embedded slides from the post-treatment biopsy. If imaging guided core needle biopsies are necessary, three to four specimens using an 18-gauge needle are required to obtain sufficient biopsy material from the pre-treatment biopsy. Two to three specimens using an 18-gauge needle are required to obtain sufficient biopsy material from the post-treatment biopsy.

Please refer to the Sample Collection Information Sheet for sample destination and shipping details.

DFCI:

Study teams will also refer to the Cross-Sectional Interventional Radiology (CSIR) Service Biopsy Protocol for this study.

Non-DFCI Sites:

Study teams will follow institutional procedures for scheduling, obtaining, and transporting biopsy specimens. All specific requirements related to DFCI personnel are limited to patients at DFCI and are not required to be completed for subjects enrolled at other sites.

Breakdown:

Pre-Treatment

Set	Needle	# Samples	Preparation (Media)	Destination
1	18G	3-4 specimens	1 specimen DMEM	DFCI Med Onc Labs ([name])
			2-3 specimens 10% neutral formalin	MGH Med Onc Labs ([name])

Post-Treatment

Set	Needle	# Samples	Preparation (Media)	Destination
1	18G	2-3 specimens	1 specimen DMEM	DFCI Med Onc Labs ([name])
			1-2 specimens 10% neutral formalin	MGH Med Onc Labs ([name])

STUDY CALENDAR

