3.1 Eligibility Criteria

- 3.1.1 Participants must have histologically or cytologically confirmed stage IV uveal melanoma.
- 3.1.2 Participants must have measurable disease, defined as at least one lesion that can be accurately measured in at least one dimension (longest diameter to be recorded for non-nodal lesions and short axis for nodal lesions) as ≥ 20 mm with conventional techniques or as ≥ 10 mm with spiral CT scan, MRI, or calipers by clinical exam. See Section 11 for the evaluation of measurable disease.
- 3.1.3 Patients can have received any number of prior therapies for treatment of their uveal melanoma excluding prior treatment with an ERK inhibitor. Patients who have received prior MEK inhibition or other MAPK targeted agents will be allowed on study.
- 3.1.4 Age ≥ 18 years of age.
- 3.1.5 ECOG performance status ≤ 2 (Karnofsky $\geq 60\%$, see Appendix A)
- 3.1.6 Life expectancy of greater than 6 months
- 3.1.7 Participants must have normal organ and marrow function as defined below:
- leukocytes $\geq 3,000/\text{mcL}$
 - hemoglobin $\geq 9.0 \text{ g/dL}$
 - absolute neutrophil count $\geq 1,500/\text{mcL}$
 - platelets $\geq 100,000/\text{mcL}$
 - total bilirubin $\leq 1.5 \times$ institutional upper limit of normal
 - AST(SGOT)/ALT(SGPT) $\leq 2.5 \times$ institutional upper limit of normal, unless there is known liver involvement in which case $\leq 5.0 \times$ institutional upper limit of normal
 - creatinine within normal institutional limits

OR

- creatinine clearance ≥ 60 mL/min/1.73 m² for participants with creatinine levels above institutional normal.
- 3.1.8 Participants must have adequate cardiac function, e.g. left ventricular ejection fraction (LVEF) of >50% as assessed by multi-gated acquisition (MUGA) or ultrasound/echocardiography (ECHO); corrected QT interval (QTc) <470ms.
- 3.1.9 Presence of metastatic disease that would be amenable to the required biopsies. Ideally pre and post biopsies should be from the same lesion and otherwise from lesions in the same organ. If not possible, then biopsy of the lesions in different organs will be permitted. Archival tissue from a biopsy taken within 6 months prior to the first study treatment may be used in place of a pre-treatment biopsy at the discretion of the principal investigator.

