3.2 Exclusion Criteria

- 3.2.1 Participants who have had chemotherapy or radiotherapy within 4 weeks (6 weeks for nitrosoureas or mitomycin C), small molecule targeted therapy (i.e. – kinase inhibitors) within 3 weeks or the last dose of antibody therapy within 4 weeks prior to entering the study or those who have not recovered from adverse events due to agents administered more than 4 weeks earlier.
- 3.2.2 Participants who are receiving any other investigational agents.
- 3.2.3 Major surgery within 4 weeks of the first dose of BVD-523. Tumor embolization procedure or ablation procedure within 2 weeks of first dose of BVD-523.
- 3.2.4 Participants with known brain metastases or evidence of leptomeningeal involvement are eligible only if these lesions are treated and both clinically and radiographically stable for at least four weeks. Patients are eligible if they are being treated with a stable dosage of steroids/anticonvulsants, requiring no dose increase for 4 weeks.

- 3.2.5 History of allergic reactions attributed to compounds of similar chemical or biologic composition to BVD-523.
- 3.2.6 Participants receiving any medications or substances that are known to be strong inhibitors of CYP1A2, CYP2D6, and CYP3A4 or strong inducers of CYP3A4 are ineligible. Because the lists of these agents are constantly changing, it is important to regularly consult a frequently-updated list such as <http://medicine.iupui.edu/clinpharm/ddis/table.aspx>; medical reference texts such as the Physicians' Desk Reference may also provide this information. As part of the enrollment/informed consent procedures, the patient will be counseled on the risk of interactions with other agents, and what to do if new medications need to be prescribed or if the patient is considering a new over-the-counter medicine or herbal product.
- 3.2.7 Uncontrolled intercurrent illness including, but not limited to, ongoing or active infection, symptomatic congestive heart failure, unstable angina pectoris, cardiac arrhythmia, or psychiatric illness/social situations that would limit compliance with study requirements.
- 3.2.8 Pregnant women are excluded from this study because BVD-523 is an ERK with the potential for teratogenic or abortifacient effects. Because there is an unknown but potential risk for adverse events in nursing infants secondary to treatment of the mother with BVD-523 breastfeeding should be discontinued if the mother is treated with BVD-523.

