Association between GNAQ mutation and outcome. To explore the association between GNAQ mutation and clinical outcome, tumors will be classified according to whether or not there is GNAQ mutation and compared with therapeutic response. The relationship between GNAQ mutation and progression-free survival will be explored using the method of Kaplan-Meier. Time to disease progression will be calculated, stratified by GNAQ mutation status.

Association between changes in levels of GNAQ, GNA11 or ERK effectors and outcome. Changes

in GNAQ or GNA11 expression, or change in ERK targets, will be documented with immunohistochemistry of tumor. Biopsies and blood/serum samples will be collected pre-treatment and 12-16 days after first treatment. Pre-treatment levels will be considered as predictors of clinical efficacy; changes in expression between pre- and post-treatment samples will also be related with clinical outcome. Pre-treatment levels and percent changes will be summarized using descriptive statistics.

For the analysis of association between change in biomarkers levels and response, we anticipate that approximately 90% of patients will have tissue for analysis at pre-treatment and again at 12-16 days, resulting in a potential sample size of 23 patients with paired biopsies. For a response rate of 0.25, this would result in six patients with response and 17 non-responders. Comparisons of biomarker change measured on a continuous scale will be based on two-sided Wilcoxon rank-sum tests with a type-I error of 0.1. There will be at least 80% power to detect differences in biomarker change that are approximately 1.35 times the common standard deviation of the change.

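### Section 13.6 pools all biopsy pairs, although in some of them other anticancer therapy may fall between the baseline sample and the first dose; for those pairs the change cannot be read as the effect of BVD-523 alone

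*Combined protocol and SAP*

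**What the plan says.** Secondary objective 3 (Section 1.3) is a pharmacodynamic comparison of pre- and on-treatment biopsies. Section 2.4 gives its purpose as finding out whether BVD-523 inhibits signalling downstream of ERK.

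- **Baseline tissue.** The default is a biopsy within the 28 days before the first dose (Sections 5.2.1 and 9.0, calendar footnote i). As a substitute, "Archival tissue from a biopsy taken within 6 months prior to the first study treatment may be used in place of a pre-treatment biopsy". The same sentence makes this subject to the PI's discretion ("may be used in place of a pre-treatment biopsy at the discretion of the PI"). Section 3.1.9 repeats the rule ("may be used in place of a pre-treatment biopsy at the discretion of the principal investigator"), as do Section 5.2.1 and footnote i. None of the four places gives a criterion for that discretion or mentions therapy given after the archival biopsy.
- **Prior therapy.** Section 3.1.3: "Patients can have received any number of prior therapies for treatment of their uveal melanoma excluding prior treatment with an ERK inhibitor", and "Patients who have received prior MEK inhibition or other MAPK targeted agents will be allowed on study".
- **Washout.** Section 3.2.1 excludes "small molecule targeted therapy (i.e. – kinase inhibitors) within 3 weeks" of entering the study, and chemotherapy, radiotherapy or antibody therapy within 4 weeks. Section 3.2.3 excludes embolization or ablation within 2 weeks of the first dose.
- **Analysis.** Section 13.6: "changes in expression between pre- and post-treatment samples will also be related with clinical outcome". Percent changes are summarized descriptively. Responders and non-responders are compared by a two-sided Wilcoxon rank-sum test at 0.10, with 23 pairs expected. No distinction is made by tissue type or by therapy given in between.

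**The concern.** A pre/on-treatment difference in a single-arm trial isolates the study drug only if little else happened between the two samples. The washout limits therapy close to entry; it does not bar therapy after the baseline sample was taken. A patient can have a biopsy, then months of a MEK inhibitor, then stop for 3 weeks and start BVD-523, all within the rules.

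The readouts are pRSK, DUSP, cyclin D and RNA sequencing, which lie on or downstream of the pathway such drugs act on. Section 2.3 itself reports MEK-dependent gene expression changes in response to MEK-inhibitor therapy in this disease. For such a pair the observed change is the sum of the earlier therapy's residual effect, tumour evolution and the BVD-523 effect, and there is no control arm to separate them. What is at stake is whether secondary objective 3 can be answered as worded.

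**Working it through.** **1. Length of the gap.** Treating entry as the first dose, which gives upper bounds:
- Archival baseline, kinase inhibitor: 6 months is about 26 weeks; 26 - 3 = about 23 weeks of possible therapy in between.
- Archival baseline, chemotherapy or antibody: 26 - 4 = about 22 weeks.
- Fresh baseline at day -28, kinase inhibitor stopped at day -21: 28 - 21 = up to 7 days in between. A fresh sample is therefore not clean by definition.

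**2. The plan's own power figure (Section 13.6).** Pairs: 0.90 × 25 = 22.5, taken as 23. Responders: 0.25 × 23 = 5.75, taken as 6, leaving 17. Exact-null Wilcoxon rank-sum, normal data, two-sided 0.10, difference 1.35 SD, by simulation: power 82% at an attained level of 0.087. The plan's figure of at least 80% is reproduced.

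**3. Bias in the pharmacodynamic change.** If BVD-523 has no effect and a share f of pairs carries a shift of d SD from earlier therapy, the expected mean change is f × d SD. The documents give neither f nor d; both are assumed here, with d = 1. Section 13.6 plans no test of mean change, so the last column only illustrates how a reader could be misled (paired t-test, 23 pairs, two-sided 0.10).

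| f | bias (SD) | false finding of a change |
|---|---|---|
| 10% | 0.1 | 13% |
| 20% | 0.2 | 22% |
| 30% | 0.3 | 35% |
| 50% | 0.5 | 66% |

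**4. Responder comparison: keep or drop the affected pairs?** Same test, difference 1.35 SD. Kept pairs carry an assumed extra disturbance with mean zero and the SD shown; dropping assumes the responder splits shown.

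| share affected | kept (6 v 17) | dropped |
|---|---|---|
| 20% | 77% (extra SD 1) | 66% (4 v 14) |
| 25% | 75% (extra SD 1); 70% (extra SD 1.5) | 65% (4 v 13) to 72% (5 v 12) |
| 50% | 69% (extra SD 1) | 56% (3 v 9) |

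Dropping gives lower power in every row, except that at 25% with the larger disturbance the two are about equal. The reference value with 23 clean pairs is 82%.

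**5. Are the needed dates captured?** Sections 5.2.1 and 5.4 collect medications from 14 days before Cycle 1 Day 1. A kinase inhibitor stopped 3 weeks before entry lies outside that window. Medical history is taken at screening, but nothing in the documents says that prior-therapy dates or the archival biopsy date are recorded for analysis.

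**The case against.** The strongest reply is that fresh biopsy is the default, substitution needs the PI's agreement, and few pairs may be affected. The first two points are correct and narrow the issue. A reader might infer that the whole paired comparison cannot be attributed to BVD-523. The documents do not support that: the problem attaches only to pairs with therapy between the baseline sample and the first dose, and their share is not given. The discretion does not close the gap, though, because no criterion comes with it. If few pairs are affected, the fix also costs little.

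A second reply is that excluding pairs from an analysis of 23 does more harm than good. For the responder comparison this largely stands (step 4). A reader might infer that affected pairs should be dropped there to protect power; the calculation points the other way. The case for separating them is attribution, and it applies to the summary of change on BVD-523.

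Third, the change is only summarized descriptively, in one secondary correlative analysis of a trial of at most 25 patients. That is so, and it limits the importance of the point. A descriptive mean or median change is still biased if it mixes two drugs' effects.

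**Conclusion.** The point holds for a defined subset. Where anticancer therapy fell between the baseline sample and the first dose, the change does not isolate BVD-523, and the plan neither identifies those pairs nor separates them. The gap can reach about 23 weeks for an archival sample and about 7 days for a fresh one.

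The size of the effect on the results cannot be determined from the documents. With an assumed 1 SD shift, the bias in the mean change is 0.1 to 0.5 SD for shares of 10% to 50%; its direction is unknown. For the responder comparison, assumed zero-mean disturbances with SD 1 to 1.5 in 20% to 50% of pairs lower power from 82% to between 77% and 69%, and excluding those pairs does not recover it.

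This is a cheap improvement that affects a secondary correlative objective only. The primary response-rate design and its decision rule are not touched.

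**What to change.** In Section 13.6, with the matching data item on the case report form:

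1. Record for each pair the date of the baseline sample, the tissue type (fresh or archival), and whether systemic anticancer therapy, or local therapy to the biopsied lesion, was given after that sample and before the first dose. Apply the flag to fresh and archival samples alike.
2. Base the pharmacodynamic summary of change on BVD-523 (secondary objective 3) on pairs without such therapy. Show all pairs alongside, with the number in each set.
3. Keep all pairs in the responder comparison, and prespecify the clean-pair subset as a sensitivity analysis, stating its reduced power (for example 66% at 4 v 14).
4. State that archival tissue remains usable for GNAQ/GNA11 testing and sequencing whatever the flag.

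Settle this before the biomarker data are seen, so that the choice of pairs cannot depend on the results.

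Cost: a few lines of analysis text, one added data item, and fewer than 23 pairs in the pharmacodynamic summary. No patient needs an additional biopsy, and eligibility is unchanged.

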10.1 Study Calendar

Baseline evaluations are to be conducted within 21 days prior to start of protocol therapy. The informed consent document must be signed within 30 days of Cycle 1 Day 1. Scans and pre-treatment biopsy may be done ≤ 4 weeks prior to the start of therapy. In the event that the participant's condition is deteriorating, laboratory evaluations should be repeated within 48 hours prior to initiation of study therapy. **Note:** Cycle 1 Day 1 labs do not need to re-meet eligibility.

Assessments must be performed prior to administration of any study agent. Study assessments and agents should be administered within ± 3 days of the protocol-specified date, unless otherwise noted.

		Cycle 1 ^B		Cycle 2 ^B		Cycle 3+ ^B	Off Treatment/ Follow-up
	Pre-Study	Day 1	Day 15	Day 1	Days 22 to 28	Day 1	EOT ^e
BVD-523		A	A	A	A	A	
Informed consent	X						
Demographics	X						
Medical history	X						
Concomitant Medications	X	X					X
Physical exam	X	X		X		X	X
Vital signs ^a	X	X		X		X	X
Height	X						
Weight	X	X		X		X	X
Performance status	X	X		X		X	X
Hematology ^b	X	X		X		X	X
Serum chemistry ^c	X	X		X		X	X
Serum lipase and amylase	X	X		X		X	X
PT and apTT	X			X		X	X
Urinalysis	X			X		X	X
B-HCG ^d	X	X		X		X	X
PK blood sample			X ^h				
ECG ^f	X	X		X		X	X
MUGA/ECHO	X	X ^g					
Adverse event evaluation		X					X
Tumor measurements	X	Tumor measurements will be repeated every 8 weeks ± 1 week from CID1.					X

Radiologic evaluation	X	Radiological imaging studies to evaluate tumor status will be repeated every 8 weeks \pm 1 week from C1D1.				X
Tumor Biopsy	X ⁱ		X			
Eye Exam ^j	X	Eye Exams should be performed every 5 weeks (\pm1 week) from C1D1.				X ^j

A: BVD-523: Dose as assigned; dispensed on this day, drug taken twice daily every 12 hours (\pm2 hours). On C1D15 the morning dose will be in-clinic due to PK sampling and it is allowable to have that dose out of the 12 (\pm2) hour window. Dosing should resume at the normal time that evening.
 
B: Window of \pm3 days for all study visits. See Section 5 for study visit details.
 
a: Vital signs to include heart rate, blood pressure, temperature, respiratory rate
 
b: Hematology Labs: hemoglobin, hematocrit, red blood cell count, white blood cell count with differential and platelet count.
 
c: Serum Chemistry Labs: Sodium, potassium, chloride, bicarbonate, magnesium, calcium, phosphorus, blood urea nitrogen, creatinine, glucose (random), total bilirubin, LDH, total protein, ALP, ALT, AST, creatine phosphokinase, and albumin.
 
d: Serum pregnancy test (women of childbearing potential only)
 
e: End of Treatment: Evaluation to be completed within 20 to 30 days after the last dose of study drug. After this visit, participant survival information will be collected, preferably via office visit or telephone contact, every 4 weeks (\pm 1 week) from the date of last dose of study drug until the participant's death or until the participant is lost to follow-up, or until study closure (approximately 6 months after the last participant terminates treatment).
 
f: 12-lead ECG. If an ECG shows QTc prolongation ($>$470 ms), the ECG must be repeated twice to obtain values in triplicate. Bazett's formula is acceptable to use to calculate the heart rate-corrected QT interval.
 
g: Unscheduled ECHOs can be completed as clinically indicated.
 
h: A blood sample for PK analysis will be drawn at time 0 (shortly before dosing). Refer to the Sample Collection Information Sheet for PK processing instructions.
 
i: The pre-treatment biopsy must be performed 1 – 28 days prior to receiving the first dose of study treatment. Archival tissue from a biopsy taken within 6 months prior the first study treatment may be used in place of a pre-treatment biopsy at the discretion of the PI. The on-treatment biopsy should be performed within Days 12 – 18 of the study.
 
j: There is a window of \pm 1 week for eye exams. The EOT eye exam should occur 5 weeks (\pm1 week) after the last dose of study drug.
						

MEASUREMENT OF EFFECT

As response is the primary endpoint of this trial, participants with measurable and/or non-measurable disease will be assessed by RECIST criteria. For the purposes of this study, participants should be reevaluated every 8 weeks. In addition to a baseline scan, confirmatory scans should also be obtained no earlier than 4 weeks following initial documentation of an objective response.

